#### 10.42 General reporting instructions

The Mayo IND Coordinator will assist the sponsor-investigator in the processing of expedited adverse events and forwarding of suspected unexpected serious adverse reactions (SUSARs) to the FDA and IRB.

Submit the Medwatch form and the CIOMS 1 form via email

[[contact]](mailto:[contact]) or [contact]) to Pharmacyclics Drug Safety, or designee, within 15 days of the event. Pharmacyclics may request follow-up and other additional information from the Sponsor Investigator.

#### 10.43 Reporting of re-occurring SAEs

ALL SERIOUS adverse events that meet the criteria outlined in table 10.41 MUST be immediately reported to the sponsor within the timeframes detailed in the corresponding table. This reporting includes, but is not limited to SAEs that re-occur again after resolution.

#### 10.5 Other Required Reporting

##### 10.51 Unanticipated Problems Involving Risks to Subjects or Others (UPIRTSOS)

Unanticipated Problems Involving Risks to Subjects or Others (UPIRTSOS) in general, include any incident, experience, or outcome that meets **all** of the following criteria:

1. Unexpected (in terms of nature, severity, or frequency) given (a) the research procedures that are described in the protocol-related documents, such as the IRB-approved research protocol and informed consent document; and (b) the characteristics of the subject population being studied;
2. Related or possibly related to participation in the research (in this guidance document, possibly related means there is a reasonable possibility that the incident, experience, or outcome may have been caused by the procedures involved in the research); and
3. Suggests that the research places subjects or others at a greater risk of harm (including physical, psychological, economic, or social harm) than was previously known or recognized.

Some unanticipated problems involve social or economic harm instead of the physical or psychological harm associated with adverse events. In other cases, unanticipated problems place subjects or others at increased *risk* of harm, but no harm occurs.

**Note:** If there is no language in the protocol indicating that pregnancy is not considered an adverse experience for this trial, and if the consent form does not indicate that subjects should not get pregnant/impregnate others, then any pregnancy in a subject/patient or a male patient's partner (spontaneously reported) which occurs during the study or within 120 days of completing the study should be reported as a UPIRTSO.

**Mayo Clinic Cancer Center (MCCC) Institutions:**

If the event meets the criteria for IRB submission as a Reportable Event/UPIRTSO, provide the Reportable Event coversheet and appropriate documentation to [[contact]](mailto:[contact]). The Mayo Regulatory Affairs Office will review and process the submission to the Mayo Clinic IRB.

**10.52 Death**

**Note: A death on study requires both routine and expedited reporting regardless of causality, unless as noted below. Attribution to treatment or other cause must be provided.**

Any death occurring within 30 days of the last dose, regardless of attribution to an agent/intervention under an IND/IDE requires expedited reporting within 24-hours.

Any death occurring greater than 30 days with an attribution of possible, probable, or definite to an agent/intervention under an IND/IDE requires expedited reporting within 24-hours.

**Reportable categories of Death**

- Death attributable to a CTCAE term.
- Death Neonatal: A disorder characterized by cessation of life during the first 28 days of life.
- Death NOS: A cessation of life that cannot be attributed to a CTCAE term associated with Grade 5.

- Sudden death NOS: A sudden (defined as instant or within one hour of the onset of symptoms) or an unobserved cessation of life that cannot be attributed to a CTCAE term associated with Grade 5.
- Death due to progressive disease should be reported as **Grade 5 “Neoplasms benign, malignant and unspecified (including cysts and polyps) – Other (Progressive Disease)”** under the system organ class (SOC) of the same name. Evidence that the death was a manifestation of underlying disease (e.g., radiological changes suggesting tumor growth or progression: clinical deterioration associated with a disease process) should be submitted.

10.53 Secondary Malignancy

- A **secondary malignancy** is a cancer caused by treatment for a previous malignancy (e.g., treatment with investigational agent/intervention, radiation or chemotherapy). A secondary malignancy is not considered a metastasis of the initial neoplasm.
- All secondary malignancies that occur following treatment with an agent under an IND/IDE will be reported. Three options are available to describe the event:
  - Leukemia secondary to oncology chemotherapy (e.g., Acute Myelocytic Leukemia [AML])
  - Myelodysplastic syndrome (MDS)
  - Treatment-related secondary malignancy
- Any malignancy possibly related to cancer treatment (including AML/MDS) should also be reported via the routine reporting mechanisms outlined in each protocol.

10.54 Second Malignancy

A second malignancy is one unrelated to the treatment of a prior malignancy (and is NOT a metastasis from the initial malignancy). Second malignancies require ONLY routine reporting unless otherwise specified.

10.55 Pregnancy, Fetal Death, and Death Neonatal

**Pregnancy reporting for Celgene/Revlimid REMS™ program**

Females of reproductive potential must adhere to scheduled pregnancy testing as required in the Revlimid REMS™ program.

Pregnancies and suspected pregnancies (including a positive pregnancy test regardless of age or disease state) of a female subject occurring while the subject is on lenalidomide, or within 28 days of the subject's last dose of lenalidomide, are considered immediately reportable events. Lenalidomide is to be discontinued

immediately. The pregnancy, suspected pregnancy, or positive pregnancy test must be reported to Celgene Drug Safety immediately by facsimile or other appropriate method using the Pregnancy Initial Report Form. The female subject should be referred to an obstetrician-gynecologist (not necessarily one with reproductive toxicity experience) or another appropriate healthcare professional for further evaluation.

The Investigator will follow the female subject until completion of the pregnancy, and must notify Celgene Drug Safety immediately about the outcome of the pregnancy (either normal or abnormal outcome) using the Pregnancy Follow-up Report Form or equivalent form.

If the outcome of the pregnancy was abnormal (e.g., spontaneous or therapeutic abortion), the Investigator should report the abnormal outcome as an AE. If the abnormal outcome meets any of the serious criteria, it must be reported as an SAE to Celgene Drug Safety immediately by facsimile, or other appropriate method, within 24 hours of the Investigator's knowledge of the event using the SAE Report Form or approved equivalent form.

All neonatal deaths that occur within 28 days of birth should be reported, without regard to causality, as SAEs. In addition, any infant death after 28 days that the Investigator suspects is related to the in utero exposure to the IP should also be reported to Celgene Drug Safety immediately by facsimile, or other appropriate method, within 24 hours of the Investigator's knowledge of the event using the SAE Report Form, or approved equivalent form.

### **Male Subjects**

If a female partner of a male subject taking investigational product becomes pregnant, the male subject taking lenalidomide should notify the Investigator, and the pregnant female partner should be advised to call their healthcare provider immediately.

### **Pregnancy reporting Mayo Clinic**

If a female subject (or female partner of a male subject) taking investigational product becomes pregnant, the subject taking should notify the Investigator, and the pregnant female should be advised to call her healthcare provider immediately. The patient should have appropriate follow-up as deemed necessary by her physician. If the baby is born with a birth defect or anomaly, a second expedited report is required.

Prior to obtaining private information about a pregnant woman and her infant, the investigator must obtain consent from the pregnant woman and the newborn infant's parent or legal guardian before any data collection can occur. A consent form will need to be submitted to the IRB for these subjects if a pregnancy occurs. If informed consent is not obtained, no information may be collected.

In cases of fetal death, miscarriage or abortion, the mother is the patient. In cases where the child/fetus experiences a serious adverse event other than fetal death, the child/fetus is the patient.

NOTE: When submitting Mayo Expedited Adverse Event Report reports for “Pregnancy”, “Pregnancy loss”, or “Neonatal loss”, the potential risk of exposure of the fetus to the investigational agent(s) or chemotherapy agent(s) should be documented in the “Description of Event” section. Include any available medical documentation. Include this form:

[http://ctep.cancer.gov/protocolDevelopment/electronic\\_applications/docs/PregnancyReportFormUpdated.pdf](http://ctep.cancer.gov/protocolDevelopment/electronic_applications/docs/PregnancyReportFormUpdated.pdf)

10.551 Pregnancy

Pregnancy should be reported in an expedited manner as **Grade 3 “Pregnancy, puerperium and perinatal conditions - Other (pregnancy)”** under the Pregnancy, puerperium and perinatal conditions SOC. Pregnancy should be followed until the outcome is known.

10.552 Fetal Death

Fetal death is defined in CTCAE as “A disorder characterized by death in utero; failure of the product of conception to show evidence of respiration, heartbeat, or definite movement of a voluntary muscle after expulsion from the uterus, without possibility of resuscitation.”

Any fetal death should be reported expeditiously, as **Grade 4 “Pregnancy, puerperium and perinatal conditions - Other (pregnancy loss)”** under the Pregnancy, puerperium and perinatal conditions SOC.

10.553 Death Neonatal

Neonatal death, defined in CTCAE as “A disorder characterized by cessation of life occurring during the first 28 days of life” that is felt by the investigator to be at least possibly due to the investigational agent/intervention, should be reported expeditiously.

A neonatal death should be reported expeditiously as **Grade 4 “General disorders and administration - Other (neonatal loss)”** under the General disorders and administration SOC.

## 10.6 Required Routine Reporting

### 10.61 Baseline and Adverse Events Evaluations

Pretreatment symptoms/conditions to be graded at baseline and adverse events to be graded at each evaluation.

Grading is per CTCAE v4.0 **unless** alternate grading is indicated in the table below:

System Organ Class (SOC)	Adverse event/Symptoms	Baseline	Each evaluation
Blood and lymphatic system disorders	Anemia		X
Skin and subcutaneous tissue disorder	Rash Maculo-papular		X*
General disorders and administration site conditions	Infusion related reaction		X
	Injection site reaction		X
	Fatigue	X	X
Investigations	Neutrophil count decreased		X
	Platelet count decreased		X

\*Only for evaluations during cycles 4-15

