### 3.0 Patient Eligibility

#### 3.1 Inclusion Criteria

- 3.11 Age  $\geq$ 18 years and considered transplant eligible.
- 3.12 Diagnosis: Pathologically confirmed diagnosis of multiple myeloma who are transplant eligible and have received any prior induction therapy (with or without maintenance).
- 3.13 Measurable MRD in bone marrow within 28 days prior to registration (MPF method)
- 3.14 ECOG Performance Status (PS) 0, 1, or 2 (Appendix I) at registration.
- 3.15 The following laboratory values obtained  $\leq$ 14 days prior to registration:
  - Absolute neutrophil count (ANC)  $\geq$ 1,000 cell/mm^3 without growth factor support
  - Platelets  $\geq$ 50,000 cells/mm^3 for patients who have bone marrow plasmacytosis  $<$ 50% or  $\geq$ 30,000 cells/mm^3 for patients who have bone marrow plasmacytosis of  $\geq$ 50%
  - Calculated or measured creatinine clearance  $\geq$ 30 ml/min (see Appendix II)
  - Total bilirubin  $\leq$ 1.5 x upper limit of normal (ULN) unless due to Gilbert's syndrome, in which case the direct bilirubin must be  $\leq$ 1.5 X ULN.
  - Aspartate aminotransferase (AST)/SGOT and alanine aminotransferase (ALT)/SGPT  $\leq$ 3 x ULN
  - PT/INR  $\leq$ 1.5 X ULN
  - Negative Urine or serum pregnancy test for women of childbearing potential.  
NOTE: Females of reproductive potential must adhere to the scheduled pregnancy testing as required in the Revlimid REMS® program.
- 3.16 Provide informed written consent.
- 3.17 Measureable disease of multiple myeloma as defined in section 11.1 at the time specified by one of the following:
  - If no relapse prior to transplant, values obtained at the time of diagnosis
  - If disease relapse prior to transplant and the patient did not have treatment for the relapsed disease prior to transplant, the values obtained at the time of relapse immediately prior to the transplant.
  - If disease relapse prior to transplant and the patient did have treatment for the relapsed disease prior to transplant, the values obtained prior to this therapy, ie, the time of relapse.

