When the study has been permanently closed to patient enrollment, submission of annual IRB approvals to the Registration Office is no longer necessary.

- 6.14 Treatment on this protocol must commence at Mayo Clinic under the supervision of a medical oncologist/hematologist.
- 6.15 Treatment cannot begin prior to registration and must begin  $\leq$  28 days after registration.
- 6.16 Pretreatment tests/procedures (see Section 4.0) must be completed within the guidelines specified on the test schedule.
- 6.17 All required baseline symptoms (see Section 10.6) must be documented and graded.
- 6.18 Study drug is available on site.

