**unless otherwise specified ← ←**

CTCAE System/Organ/Class (SOC)	ADVERSE EVENT	AGENT	ACTION**
Investigations	Neutrophil count decreased Grade 4 lasting >7 days	Daratumumab	Hold (Day 1) or Omit (Days 8, 15, or 22) Daratumumab ** until recovery to Grade ≤2 or baseline May restart at same dose at the next planned dosing date.
	Platelet count decreased Grade ≥3 with bleeding		
Blood and lymphatic system disorders	Febrile neutropenia ≥Grade 3		Hold (Day 1) or Omit (Days 8, 15, or 22) Daratumumab ** until recovery to Grade ≤2 or baseline May restart at same dose at the next planned dosing date.
	Neutropenia with infection, of any grade		
Gastrointestinal disorders	Nausea Grade 2 (if persistent for >7 days despite optimal antiemetic therapy)		Hold (Day 1) or Omit (Days 8, 15, or 22) Daratumumab ** until recovery to Grade ≤1 or baseline May restart at same dose at the next planned dosing date.
	Vomiting ≥Grade 3 (if persistent for >7 days despite optimal antiemetic therapy)		
	Diarrhea ≥Grade 3 (if persistent for >7 days despite optimal anti-diarrheal therapy)		
Other (Non-hematologic)****	Any other Grade 4 AE or any unmanageable Grade 3 AE that was present at baseline or lasts for >7 days after the last administration of daratumumab		Hold (Day 1) or Omit (Days 8, 15, or 22) Daratumumab ** until recovery to Grade ≤1 or baseline May restart at same dose at the next planned dosing date.

Additional Adverse Events:

\*\* If Daratumumab is omitted in the middle of the cycle and the toxicity resolves, patient can re-start the drug but the days of drug treatment missed do not need to be caught-up and can be omitted in order to maintain the cycle schedule.

- Dose omission: Daratumumab may be omitted for adverse event considerations for a maximum of 28 consecutive days during Consolidation 1 (Cycle 1-2 or 1-4, as the case may be for that patient). Patients on maintenance therapy may be continued on treatment with single-agent daratumumab or lenalidomide in case the other agent has to be permanently discontinued in absence of disease progression. If a patient on maintenance treatment must discontinue both,

lenalidomide and daratumumab, they should be removed from the protocol therapy and proceed to event monitoring.

- If multiple adverse events are seen, administer dose based on the greatest reduction required by any single adverse event observed.

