#### 16.42 Secondary Outcome Analyses

The rate of MRD negative response after pre-SCT consolidation with Daratumumab will be estimated by the number of patients who achieve MRD negative status by flow cytometry (MPF) in the bone marrow after pre-SCT consolidation with Daratumumab divided by the total number of evaluable patients. Exact binomial 95% confidence intervals for the true rate of MRD negative response after pre-SCT consolidation with Daratumumab will be calculated.

The rate of MRD negative response after 1 year (12 cycles) of Daratumumab and lenalidomide maintenance will be estimated by the number of patients who achieve MRD negative status by flow cytometry (MPF) in the bone marrow after 1 year of maintenance therapy divided by the total number of evaluable patients. Exact binomial 95% confidence intervals for the true rate of MRD negative response after 1 year of maintenance will be calculated.

Progression-free survival time is defined as the time from registration to the time of progression or death due to any cause. Patients who are alive and progression-free will be censored on the date of their last disease assessment. Patients who receive subsequent treatment for myeloma before disease progression will be censored on the date of their last disease assessment prior to initiation of the subsequent treatment. The distribution of progression-free survival will be estimated using the method of Kaplan-Meier.

Survival time is defined as the time from registration to death due to any cause. The distribution of survival time will be estimated using the method of Kaplan-Meier.

The overall response rate at day 100 post ASCT will be estimated by the number of patients with an objective status of sCR, CR, VGPR, or PR at the day 100 post ASCT assessment divided by the total number of evaluable patients. Response assessment will be in comparison to values obtained at the disease assessment at the time registration. Exact binomial 95% confidence intervals for the true overall response rate at day 100 post ASCT will be calculated.

**Adverse Events:** All eligible patients that have initiated treatment will be considered evaluable for assessing adverse event rate(s). The maximum grade for each type of adverse event will be recorded for each patient, and frequency tables will be reviewed to determine patterns. Additionally, the relationship of the adverse event(s) to the study treatment will be taken into consideration.

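### Blood counts are not graded at baseline and toxicity is tabulated as worst grade, so a cytopenia that persists from entry would inflate the hematologic adverse event rates; a minor defect, repairable from existing data

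*Combined protocol and SAP*

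**What the plan says.** Section 10.61 begins with a general instruction: "Pretreatment symptoms/conditions to be graded at baseline and adverse events to be graded at each evaluation". The table beneath it decides which terms this covers. Fatigue is ticked for both baseline and each evaluation. The rows "Neutrophil count decreased X" and "Platelet count decreased X" each carry a single tick, in the each-evaluation column, and so does anemia.

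Section 6.17, in the registration procedures, does not widen the list. It states "All required baseline symptoms (see Section 10.6) must be documented and graded", which leads back to the same table.

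Section 3.15 sets the entry counts: ANC at least 1,000/mm³ and platelets at least 50,000/mm³. A lower platelet limit of 30,000/mm³ is reserved "for patients who have bone marrow plasmacytosis" of 50% or more. No hemoglobin limit is listed.

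The adverse events paragraph of section 16.42 sets the summary: "The maximum grade for each type of adverse event will be recorded for each patient". Frequency tables follow, and relationship to treatment is also to be considered. The paragraph has no worsening-from-baseline rule, no definition of a treatment-emergent event and no shift table.

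**The concern.** Objective 2.24 is the safety profile of the regimen. With one arm, each patient's own baseline is the only internal reference for separating what treatment did from what the disease and earlier therapy had already done. The eligibility criteria expect some patients to enter with low counts, and section 1.1 names anemia as a consequence of marrow displacement by myeloma.

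If such a count is still low at an on-study evaluation, it receives a grade and enters the worst-grade table with no baseline grade beside it. The three hematologic terms also bypass the grade and attribution filters of section 10.62, because those filters apply only to events not already named in section 10.6. At stake is an upward bias in the reported rates of anemia, neutropenia and thrombocytopenia.

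**Working it through.** The plan gives no figure for this point, so there is none to reproduce. The check has two steps.

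**Step 1: the passages side by side.**

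| Item | Graded at baseline (10.61) | Graded on study (10.61) | Entry limit (3.15) |
|---|---|---|---|
| Fatigue | yes | yes | not applicable |
| Anemia | no | yes | none listed |
| Neutrophils | no | yes | ANC ≥ 1,000/mm³ |
| Platelets | no | yes | ≥ 50,000/mm³; ≥ 30,000/mm³ if plasmacytosis ≥ 50% |

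Section 16.42 takes the worst on-study grade for each term. Nothing between entry and that table removes a grade the patient already had.

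**Step 2: direction and size.** Let b be the share of patients who enter at or above a given grade. Let t be the rate at which patients reach that grade on treatment, taken as the same whether or not they entered with it. Suppose the entry cytopenia persists to at least one evaluation.

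- Tabulated rate = b + (1 − b)t
- Inflation = b + (1 − b)t − t = b(1 − t)

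Neither b nor t is in the documents, so the values below are assumptions that show a range (inflation in percentage points, tabulated rate in brackets):

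| | b = 5% | b = 10% | b = 20% |
|---|---|---|---|
| t = 10% | 4.5 (14.5%) | 9 (19%) | 18 (28%) |
| t = 20% | 4 (24%) | 8 (28%) | 16 (36%) |
| t = 80% | 1 (81%) | 2 (82%) | 4 (84%) |

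For the 45 evaluable patients planned in section 16.12:

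- t = 20%: 0.04 × 45 = 1.8 to 0.16 × 45 = 7.2 patients, about 2 to 7.
- t = 80%: 0.01 × 45 = 0.45 to 0.04 × 45 = 1.8 patients, at most about 2.

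The sign is upward whenever b > 0 and t < 1, whichever grade is considered. The size depends on quantities the plan does not supply. If patients who enter with low counts are also more likely to reach the grade on treatment, the inflation is smaller than shown.

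**The case against.** The strongest reply is that nothing is lost. The test schedule in section 4.1 requires a CBC with differential within 14 days before registration. Laboratory grades follow from the counts, so a baseline grade can be derived at any time. The layout of the 10.61 table may reflect this, since fatigue has no laboratory source and infusion or injection-site reactions cannot precede dosing. Attribution is considered in 16.42, and section 10.3 includes categories for unlikely and unrelated. The schedule also marks adverse event monitoring before registration.

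Much of this stands, and it makes the defect repairable. It does not remove it. Nothing in 16.42 commits anyone to derive the baseline grades or use them. No attribution-restricted table is defined. The pre-registration monitoring entry does not say that blood-count terms are graded then.

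A second reply concerns size. Transplant is part of protocol treatment, and the engraftment thresholds in section 11.6 (ANC above 500/mm³, untransfused platelets above 20,000/mm³) imply deep nadirs. Where these are captured, t is high and entry counts hardly move the worst grade. That stands as a limit on magnitude. The plan does not settle whether they are captured: the schedule has no visit column between the pre-transplant visit and the Day 100 visit.

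A reader might infer more than the documents support:

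- That the plan says entry cytopenias are to be counted as toxicity. It is silent; the counting follows from applying its rules as written.
- That the two sources can never be separated. The pre-registration CBC allows it.
- That the dose rules in section 8.3, which use "until recovery to Grade ≤2 or baseline", rest on a missing value. The same CBC supplies the baseline count.
- That platelets of 30,000/mm³ are the general entry limit. That limit is conditional, and the number of patients meeting the condition is not given.
- That a particular number of Grade 3 events is added. The CTCAE cut-offs are not printed in the documents, and taking the whole of b as the inflation sets t to zero, which gives a ceiling.

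**Conclusion.** The point holds as a minor one. Followed as written, sections 10.61 and 16.42 would let a cytopenia that was present at entry and persists count in the hematologic tables for objective 2.24, with an upward bias of b(1 − t). That is 4 to 16 percentage points for b between 5% and 20% with t at 20%. It falls to 1 to 4 points if t is nearer 80%, as it could be when transplant nadirs are recorded. These values of b and t are assumptions, and persistence to an evaluation is a further one.

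No decision in the trial rests on these tables. The primary endpoint and the power table in section 16.32 depend on MRD results, and the stopping rule in section 16.52 counts only non-hematologic events. The effect is confined to descriptive safety reporting.

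**What to change.** In section 10.61, mark the baseline column for anemia, neutrophil count decreased and platelet count decreased, graded from the pre-registration CBC already required in section 4.1.

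In section 16.42, keep the current worst-grade table. Beside it add, for these three terms, a table of the worst post-baseline grade among events that exceed the patient's baseline grade. A cross-tabulation of baseline grade against worst grade would serve equally well.

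The cost is three grades per patient from an existing blood test and one extra table. No new sample, visit or patient is needed, and no clinical rule changes.
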